Phase 2: This phase consists of a 4-week low-carbohydrate calorie-restricted dietary intervention on glycemic control, body weight, body composition and energy expenditure. Overweight and obese participants with T1D from Phase 1 (n = 10) will be asked to alter their diet under the guidance of a nutritionist or registered dietitian (RD) and the medical team over a 4-week period (3 weeks outpatient self-selected, 5 days outpatient with provided meals and 2 days inpatient). After approximately 4 weeks on this diet, participants will return to the TRI-MD for re-evaluation using a protocol identical to that employed at baseline (Phase 1).

Study Agent, Device, and/or Intervention Description

The Phase 2 diet prescription will have a 500 kcal/day calorie deficit and will contain approximately 14% of calories from carbohydrate. Participants/Study Staff will perform continuous glucose monitoring via CGM or Point of Care (POC) blood glucose for the entire period so that insulin can be adjusted as necessary to prevent hypoglycemia. They will meet weekly with a nutritionist or a registered dietitian either in person or by phone and have their insulin adjusted on a daily basis or as needed in consultation with the PI and the medical staff of the TRI.

Twenty-four hour heart rate monitoring will be performed simultaneously with energy expenditure measurements in the chamber to allow calibration and refinement of the model for free-living energy expenditure we will derive in patients with type 1 diabetes. As such, this data is not a primary or secondary endpoint, but is considered exploratory. Heart rate data from wearable devices could then be used, along with age, sex, HbA1c and estimates of body composition to provide more accurate estimates of energy requirements for dietary interventions, for example. There are no safety issues that require heart rate monitoring in this particular population or study. We do not anticipate any output from this monitoring that would require real-time monitoring, consequently, we will only use the device to capture data for subsequent downloading.

Study Site(s)/Location(s) and Number of Subjects

This study will be conducted by Investigators at the Florida Hospital Translational Research Institute for Metabolism and Diabetes (TRI-MD). All study visits will take place at the TRI-MD facility. This study represents one aim of a multicenter NIH grant awarded to UNC Chapel Hill on which [name] is a PI and [name] is a Co- PI.

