A comprehensive health history will be obtained utilizing a standard Demographics and Health History Form that will be implemented for all aims of the grant (See **Appendix B**). A standard physical examination will be performed by a study physician, physician assistant, or nurse practitioner.

Anthropometric Screening

Body weight (calibrated scale), height, waist and hip circumference will be obtained while in a gown, without shoes. BMI will be calculated.

Screening Labs

The laboratory assessments below (at minimum) will be used to confirm study eligibility (Inclusion/Exclusion Criteria), as well as overall health status:

- complete blood count (CBC)
- comprehensive metabolic panel (CMP)
- HbA1C
- lipid panel
- thyroid function tests: thyroid stimulating hormone (TSH)
- urinalysis
- urine drug test
- urine pregnancy test, for female subjects of childbearing potential

Vital Sign Measurements

Measurement of vital signs will include heart rate (HR), blood pressure (BP), respirations and temperature will be measured sitting for at least 5 min.

Continuous Glucose Monitoring (CGM)

Starting at Visit 2, participants with type 1 diabetes will wear an unblinded continuous glucose monitor (CGM) for the duration of the study as a safety measure for glucose levels. Non-diabetes participants will have the CGM inserted during Visit 3 for the inpatient stay, for a data comparison. The CGM can be worn for up to 7 days at a time and will be replaced as needed. The CGM will not be worn in the MRI as the interference from CGM devices on MRI data has not been tested. It will be removed up to several days prior to the MRI and replaced after the MRI is completed. During time periods where blood glucose data is not available for CGM, point of care testing will continue.

The continuous glucose monitor will be placed by a member of the study team and participants will be instructed on the use and removal of the device, as well as reinsertion of the device as needed. During CGM wear, participants will be instructed to perform blood glucose

measurements approximately every 12 hours to calibrate the device, which can be completed by the participant or a trained clinical staff member. The FDA-approved system includes a sensor, transmitter, and receiver. It measures interstitial fluid glucose levels in the range of 40 mg/dl to 400 mg/dl every 5 minutes for up to 7 days.

Blood Glucose and Ketone testing

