Participants will have at least bi-weekly calls to assess maintenance of glycemic control. Furthermore, participants will be asked to check their blood sugar approximately every 12 hours plus blood ketones at least once per day. Participants will keep a log of their daily values and contact the study team immediately (see below) if values are out of range. If the ketone values are elevated (> 0.6 mmol/L) or if they display any symptoms of elevated ketone levels, they will contact the investigator immediately. Early symptoms of elevated Ketone levels include; polydipsia and polyuria several days before the onset of DKA. Other common symptoms include generalized weakness, weight loss, nausea, vomiting, and abdominal pain. Prolonged elevated levels of ketones can lead to swelling in brain, loss of consciousness, diabetic coma and death.

Contact:

Translational Research Institute for Metabolism and Diabetes [name]
[contact].

Participants are also wearing a continuous glucose monitor for the duration of the of the study that will alert them to glucose trends and allow them to take corrective/preventive action as necessary.

Participants will be provided with Hypoglycemia, Hyperglycemia (visit 2) and diabetic ketoacidosis (visit 4) information/instructions sheets

Continuous Glucose Monitor Risks: The risks of wearing the CGM are minimal. Bruising, redness, discomfort, and some bleeding can occur. Mild skin irritation is common. Rarely an infection can occur at the site of CGM sensor needle placement. Any infection, or sign of infection, will be treated immediately. An allergic reaction to the tape used to hold the sensor in place is possible. If there is pain, redness, irritation, or rash at insertion site, the sensor will be removed and re-inserted in a different site.

Protection against Risk:

- CGM placement will be conducted by qualified staff using aseptic techniques to reduce these risks. Participants will be trained on proper insertion techniques so that they can replace sensors at home as necessary.

Other Risks: In addition to the risks listed above, participants may experience a previously unknown risk or side effect. They will be asked in advance about any previous injury, which could prevent them from participating in this test.

Mitigation of Risks

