2. Two phone calls will be conducted by UNC between Day 1 through Day 7 and Day 18 through Day 35.
3. Participant will continuously wear CGM until collection at either the end of Phase 1 or Phase 2 as appropriate. The site must be changed at least every 7 days.
4. Phase II participants only
5. Food Frequency Questionnaire, Diabetes Eating Problem Survey, Dutch Eating Behavior Questionnaire, Barratt Impulsiveness Scale (BIS-15), Food Craving Inventory, Nutrition Knowledge Survey, Diabetes Quality of Life, Hypoglycemia Fear Survey (HFS), Recent Physical Activity Questionnaire (RPAQ), Sleep Disorder Questionnaire, The Center for Epidemiological Studies-Depression (CES-D)

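### CGM may be taken off up to several days before the MRI, longer than the stated reason needs; a limit at unit admission would keep it on during the last home diet days

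*Combined protocol and SAP*

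**What the plan says.** The Continuous Glucose Monitoring (CGM) section describes CGM in participants with type 1 diabetes as a safety measure worn throughout the study. It then makes an exception for imaging. The reason is "The CGM will not be worn in the MRI as the interference from CGM devices on MRI data has not been tested". The rule that follows is "It will be removed up to several days prior to the MRI and replaced after the MRI is completed". Cover for the gap comes next: "During time periods where blood glucose data is not available for CGM, point of care testing will continue".

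Two other places describe CGM wear without mentioning this exception:

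- Potential Risks, under the low-carbohydrate diet, lists among the protections: "Participants are also wearing a continuous glucose monitor for the duration of the of the study that will alert them to glucose trends".
- Appendix A, footnote 3: "Participant will continuously wear CGM until collection at either the end of Phase 1 or Phase 2 as appropriate".

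The section on the study agent and intervention is more flexible. For Phase 2 it accepts either CGM or point-of-care (POC) glucose over the whole period, so that insulin can be adjusted.

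**The concern.** The reason and the rule do not match. A concern about interference in the scanner supports taking the sensor off before the participant enters it. It does not explain a removal days earlier, and no other reason is given. The word several has no number attached.

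The timing gives this some weight in Phase 2. The MRI is listed for Day 38 and admission to the Clinical Research Unit (CRU) is on the evening of Day 37. The days just before that are spent at home on provided food with 14% of calories from carbohydrate and a 500 kcal deficit. The risk section names hypoglycemia and diabetic ketoacidosis as the hazards of this diet, and CGM alerts are one of the listed protections.

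There is also a smaller data cost. Glycemic control is part of the secondary objective, and Appendix A schedules HbA1c only at screening. Any description of glycemia on the diet therefore rests on CGM and POC values.

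**Working it through.** The plan gives no figure to reproduce, so the check counts the days that the rule could remove.

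**Inputs**

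- Listed MRI days: Day 9 and Day 38, with a window of 2 days either side (magnetic resonance section).
- CRU admission: evening of Day 8 and of Day 37 (Study Visits).
- Provided-food home period: Day 32 to the Day 37 admission, 37 − 32 = 5 days. This agrees with Research Design, Phase 2: "5 days outpatient with provided meals and 2 days inpatient".
- All outpatient diet days: Day 11 to Day 37, 37 − 11 = 26 days.
- CGM rate: "It measures interstitial fluid glucose levels in the range of 40 mg/dl to 400 mg/dl every 5 minutes for up to 7 days". That is 24 × 60 / 5 = 288 readings a day.
- POC minimum: glucose at least twice and ketones at least once a day (Appendix A, footnote 1).
- Assumption: k, the days from removal to MRI, is 2, 3, 4 or 5. Days are whole calendar days, because no scan time is given.

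**MRI on Day 38.** Home days without CGM = 37 − (38 − k) = k − 1.

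| k | Provided-food days lost (of 5) | Outpatient diet days kept (of 26) | CGM readings lost at home |
|---|---|---|---|
| 1 | 0 | 26 (100%) | 0 |
| 2 | 1 | 25 (96%) | 288 |
| 3 | 2 | 24 (92%) | 576 |
| 4 | 3 | 23 (88%) | 864 |
| 5 | 4 | 22 (85%) | 1,152 |

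Removal one day before the MRI, which is about CRU admission, costs no provided-food home day.

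**MRI moved to Day 36.** Days lost = min(k, 36 − 32) = 2, 3, 4, 4 of 5.

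**MRI on Day 9.** By the same count, k − 1 = 1 to 4 of the 7 home days from Day 1 to Day 8 are lost. These precede the diet, so the cost is mainly in pre-diet CGM data.

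**Calorimeter stay (Days 10–11 and 39–40).** With the MRI on Day 9 or 38, the sensor goes back on before the chamber, so there is no overlap for any k. Overlap needs the MRI moved to Day 11 or 40 and, as well, removal 2 or more days earlier. The 23-hour stay, 23 × 60 / 5 = 276 readings, would then be without CGM.

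**Sensor life.** With a 7-day limit, a sensor fitted on Day 1 runs out on Day 8. One fitted on Day 9 and changed every 7 days (Days 16, 23, 30) runs out on Day 37. Both dates coincide with CRU admission.

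**The case against.** The case on the other side is substantial, and much of it stands.

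- **Glucose monitoring does not stop.** The CGM section continues POC testing in the gap, and the intervention section accepts CGM or POC throughout Phase 2. The risk section adds that "participants will be asked to check their blood sugar approximately every 12 hours plus blood ketones at least once per day". Calls are made about twice a week, and Days 32 and 35 are in-person visits. A reader might infer that participants are left unmonitored; the documents do not support that. What remains is that the stated POC frequency is not raised when CGM is off, and checks about every 12 hours cannot provide alerts. Those checks are already made while CGM is worn, so the stated minimum adds nothing to make up for the lost readings.
- **The wording is a ceiling.** Removal on the day of the scan already complies. To read it as having no limit, or as requiring early removal, goes too far. Timing might also be fixed in the study-specific procedures, which are not part of these documents.
- **There is no flat contradiction.** A reader might set the CGM section against the risk section and Appendix A as conflicting. It is better read as a specific exception that those two places fail to mention.
- **Sensor life may explain some early removal.** It could account for about one day before Day 9, though the protocol does not say so. It does not account for several days.
- **Loss of chamber glucose is improbable.** A reader might infer that the in-chamber CGM named in the Overview of Statistical Plan is at risk. On the listed MRI days it is not. The loss needs an unlikely pairing of a moved scan with early removal, and the protocol prefers the listed day.
- **The data loss is small.** Under the assumed range with the MRI on Day 38, 85% to 96% of outpatient diet days keep CGM. Phase 2 is a 10-person pilot aimed mainly at tolerability and safety, with no CGM endpoint or completeness threshold stated.

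**Conclusion.** The point holds as a minor one. The rule permits a longer period without CGM than its reason needs. Before the Day 38 MRI, that period would fall on home days when the risk section counts on CGM alerts. If removal is 2 to 5 days early, 1 to 4 of the 5 provided-food home days are affected for each Phase 2 participant.

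This size rests on an assumed meaning of several and on staff using the latitude; if they remove the sensor at admission, the loss is nil. It is the loss of one safety layer among several and of some CGM data. It does not threaten the primary energy model on the listed schedule, and it does not show that Phase 2 is unsafe.

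**What to change.** In the CGM section, replace the removal sentence with a rule along these lines:

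- CGM is removed no earlier than CRU admission (Day 8 or Day 37), or on the MRI day if the MRI is moved ahead of admission, and is refitted straight after the scan.
- If the MRI is moved to after the chamber stay (Day 11 or Day 40), CGM stays on until chamber exit.

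In the low-carbohydrate paragraph of Potential Risks and in Appendix A footnote 3, add a clause naming this short, POC-covered gap as the one exception to continuous wear.

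The cost is one sentence or two and two clauses. No visit, scan or endpoint changes. On the listed schedule the 7-day sensors run out at about admission anyway, and the gap then falls in the unit, where staff can run POC checks. When visits shift, an occasional sensor will be changed before its 7 days are up. For a scan after the chamber, CGM collection is already scheduled on Day 11 for Phase 1 only participants and on Day 40; a Phase 2 participant scanned on Day 11 would need the sensor refitted.

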Phase 1 (24 individuals with T1D with a range of body weights; 9 matched controls)

Visit 2/ Day 1 (outpatient, 1-2 hours): Participants will complete:

- AE/ Conmed Assessment
- Vital Signs
- Urine Pregnancy test
- DEXA
- CGM placement (Type 1 diabetes group only)
- Activity Monitor Distribution

Visit 2/Day 1-7 (phone call). These two questionnaires will be completed through phone interviews done by the UNC Nutrition Obesity Research Center (UNC NORC). There will be a total of two phone calls between days 1 and 7.

- 24-hour Dietary Recall
- Previous Day Physical Activity Recall

Visit 3/ Day 8-11 (inpatient): Participants will be admitted to the TRI Clinical Research Unit (CRU) for 4 days (3 nights) for a comprehensive metabolic assessment including:

Day 8: Subjects will be admitted to the CRU in the *evening* and receive a calculated weight maintaining meal.

- Check into CRU
- AE/Conmed Assessment
- Vital Signs
- Activity monitor collection
- Inpatient Standard Diet- dinner meal only and a possible snack
- Overnight stay

Day 9: Subjects will complete following:

- AE/Conmed Assessment
- Vital Signs
- Inpatient standard diet- controlled meal three times a day and a possible snack
- Fasting blood samples will be collected for archiving and lipid panel
- FibroScan®
- Whole-body Magnetic Resonance Imaging (MRI)
- Magnetic Resonance Imaging and Spectroscopy (MRI/S)
- Magnetic Resonance Elastography (MRE)
- CGM placement (initial insertion for non-diabetes group)
- Stool collection and banking
- Paper Questionnaires (**Appendices C-M**)
- Overnight stay

Day 10: Subjects will complete following:

- AE/Conmed Assessment
- Vital Signs
- Inpatient Standard Diet- controlled meal three times a day plus a possible snack.
- Check into calorimeter
- Whole Room Calorimetry for 23 hours
- Polar chest strap and Polar watch for heart rate monitoring
- Activity Monitor Distribution
- 24-hour urine collection
- Overnight stay

Day 11: Subjects will complete following:

- AE/ Conmed Assessment
- Vital Signs
- Inpatient Standard Diet- breakfast only
- Check out of calorimeter
- CGM collection (for Phase 1 only participants)
- Remove Polar chest strap and watch
- Activity Monitor collection
- Check out of CRU

Phase 2 (10 overweight/obese participants with T1D)

Visit 3/Day 11: Initial instruction in low carbohydrate, calorie restricted diet

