After exiting the calorimeter, subjects participating in Phase 2 will meet with the research registered dietitian (RD). Counseling sessions will occur weekly on day 11, 18 +/- 2 and 25 +/- 2 to review their dietary adherence and adjust recommendations as necessary to meet the diet prescription of a low carbohydrate, calorie restricted diet. Additional counseling can occur by phone during the scheduled twice-weekly phone calls. In-person sessions with the nutritionist and/or registered dietitian will include audio recording of the session. Recordings of the RD sessions will be utilized to modify and refine the low carbohydrate education materials in preparation for the study's later dietary interventions, which will happen at UNC and Stanford. Training in ketone and glucose testing for safety.

Phone Calls (Phase 2 only)

Participants will be contacted by phone from a TRI- staff member approximately twice a week to monitor glycemic control, adjust insulin as necessary, and answer any questions they may have.

Visit 4/ Day 18 ±2 (outpatient):

- AE/ Conmed Assessment
- Vital Signs
- Home blood glucose and ketone test
- Urine Pregnancy test
- Diet counseling- low carbohydrate diet

Visit 4/Day 18 +/-2 through Day 24 (phone calls).

- At least 1 call to monitor diet adherence and tolerability
- At least 2 phone calls to monitor glycemic control, adjust insulin as necessary, and answer any questions they may have.
- Home glucose and ketone testing to continue.
- Continue outpatient low carbohydrate diet (self-selected foods based on counseling)

Visit 4-7/Day 18+/-2 through Day 35 (phone calls). These two questionnaires will be completed through phone interviews done by the UNC Nutrition Obesity Research Center (UNC NORC). There will be a total of two phone calls between days 18 and 35.

- 24-hour Dietary Recall

- Previous Day Physical Activity Recall

Visit 5/ Day 25±2 (outpatient):

- AE/ Conmed Assessment
- Vital Signs
- Home blood glucose and ketone test
- Urine Pregnancy test
- Diet counseling- low carbohydrate diet

Visit 5/Day 25 +/-2 through Day 31 (phone calls).

- At least 1 call to monitor diet adherence and tolerability
- At least 2 phone calls to monitor glycemic control, adjust insulin as necessary, and answer any questions they may have.
- Daily home glucose and ketone testing to continue.
- Continue outpatient low carbohydrate diet (self-selected foods based on counseling)

Visit 6/ Day 32 (outpatient):

- AE/Conmed Assessment
- Vital Signs

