The purpose of the low carbohydrate diet counseling will be to assist young adult, overweight study participants with Type 1 diabetes in adhering to a lower calorie diet (500 calorie deficit) that contains around 14% carbohydrate, 28% protein and 58% fat (majority polyunsaturated and monounsaturated fats). Study participants will attend an initial counseling session (60- 90 minutes) from a Registered Dietitian (RD) that covers general steps for problem solving, contents of eating a general healthy diet. An introduction to using MyFitnessPal to track their intake is done at Visit 2 (Day 1) and will be utilized thru Phase 1 (optional) and Phase 2 to help participant and study team to summarize food intake. The RD will also use the participant's 24-hour recall to discuss areas where lower carbohydrate and lower calorie foods could be substituted for foods the participant eats on a regular basis. Calorie balance will also be discussed as well as recommendations for insulin bolusing as carbohydrate intake is reduced and protein and fat intake is increased. Participants will also be provided with several sample low carbohydrate, low calorie meal plans, snack ideas, and food lists. At the end of the session, participants will work with the interventionist to set reasonable goals to adhere to the new low carbohydrate, low calorie diet for the next three weeks. Sessions 2 and 3 (30 minutes) will consist of the interventionist check-in and a more in-depth discussion of low carbohydrate and low-calorie consumption, as well as a concentration on saturated verses unsaturated fats.

24-hour Dietary Recall and Previous Day Physical Activity Recall (PDPAR)

These questionnaires will both be conducted by phone and are expected to take approximately 1 hour to complete.

As part of the Metabolic Chamber study, all participants will be asked to complete two 24-hour recall interviews. The 24-hour recall is a diet assessment instrument used to enable researchers to collect diet data on foods consumed by the participant during the previous 24 hours. A subset of participants of 10 participants will be asked to complete an additional two 24-hour recalls after being instructed on and living on a low carb diet.

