- A urine pregnancy test will be done prior to scans of all women of childbearing potential (all women except those with prior hysterectomy, tubal ligation, or absence of menses for ≥ 2 years).

Magnetic Resonance Spectroscopy: There are no known biological risks associated with magnetic resonance spectroscopy. Some short-term discomfort may be experienced. The short-term risks associated with MRI are minimal, but include heating, loud noises and claustrophobia. There are some people who should not undergo MRI; the contraindication is largely based on the presence of certain metal objects within a person (i.e. pacemaker, aneurysm clip, metal fragments, etc.).

Protection against Risk:

- There will be a strict safety screening protocol, to ensure any people with contraindications are excluded from volunteering in MR portion of study
- Incidental Findings: There will be no diagnostic analysis associated with any of the MR sequences used in this protocol; the images will not be sent for radiology review. However, some of the MR images we obtain as part of this protocol may show incidental medical findings. In the case where a medical abnormality is apparent on an image, the image will first be reviewed by an investigator on this protocol. If the abnormality is confirmed, then the participant will be instructed to seek medical attention from their health care provider

Activity Monitoring: There are no risks associated with the wearing of activity monitors.

Heart Rate Monitoring: There are no risks associated with the wearing of the chest strap and Polar Watch.

Metabolic chamber: Besides inconveniences that can reasonably be expected as a result of spending an extensive time (24h) in the live-in room calorimeter, there is no risk to participants' physical health. Claustrophobia is an exclusionary criterion. All participants will be given an opportunity to experience the metabolic chamber prior to enrollment in the study.

Protection against Risk:

- Participants will be closely monitored to ensure they are comfortable while in the calorimeter.

Low Carbohydrate Diet: Low carbohydrate diets could lead to hypoglycemia and diabetic ketoacidosis (DKA).

Protection against Risk:

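### The diabetic ketoacidosis sheet is scheduled for Visit 4 (Day 18 ±2), about a week after the low-carbohydrate diet starts on Day 11

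*Combined protocol and SAP*

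**What the plan says.** Under Potential Risks, the Low Carbohydrate Diet entry names the hazard: "Low carbohydrate diets could lead to hypoglycemia and diabetic ketoacidosis (DKA"). The protections listed beneath it include home glucose and ketone checks, telephone calls, and a rule for contacting the investigator. That rule applies when ketones exceed 0.6 mmol/L "or if they display any symptoms of elevated ketone levels, they will contact the investigator immediately". The same list sets the timing of the written material: "Participants will be provided with Hypoglycemia, Hyperglycemia (visit 2) and diabetic ketoacidosis (visit 4) information/instructions sheets".

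The Study Visits section fixes the two dates that matter:

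- The diet is first taught on the last day of the Phase 1 inpatient stay: "Visit 3/Day 11: Initial instruction in low carbohydrate, calorie restricted diet". The paragraph on that session ends with "Training in ketone and glucose testing for safety".
- The visit named for the DKA sheet comes a week later: "Visit 4/ Day 18 ±2 (outpatient").

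Dietary Counseling says that at the end of the initial session participants "set reasonable goals to adhere to the new low carbohydrate, low calorie diet for the next three weeks". Research Design divides the four weeks of diet into "3 weeks outpatient self-selected, 5 days outpatient with provided meals and 2 days inpatient".

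**The concern.** A sheet that explains DKA, listed as a protection against a risk of the diet, should be in the participant's hands when the diet begins. As written, it comes at the second counseling session. The other two sheets, on hypoglycemia and hyperglycemia, are given at Visit 2, before any change of diet. Only the DKA sheet follows the exposure it is meant to cover.

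What is at stake is participant safety, not inference. From the first day of the diet, participants at home are expected to recognise symptoms of raised ketones and to call at once. The sheet is the only written DKA instruction for participants that the protocol names. In the first week they cut carbohydrate to about 14% of calories while their insulin is being adjusted, and under the text as it stands they do so without the sheet. No endpoint, model or sample-size figure depends on this.

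**Working it through.** **Inputs**

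| Item | Value | Source |
|---|---|---|
| First diet session | Visit 3, Day 11 | Study Visits, Phase 2 |
| Visit 4 | Day 18 ±2, so Day 16 to Day 20 | Study Visits, Phase 2 |
| First pick-up of provided meals | Visit 6, Day 32 | Study Visits, Phase 2 |
| Second admission | Visit 8, Day 37 (evening) | Study Visits, Phase 2 |
| Diet periods | 3 weeks + 5 days + 2 days | Research Design, Phase 2 |
| Phase 2 participants | 10 | Research Design, Phase 2 |
| DKA sheet | Visit 4 | Potential Risks, Low Carbohydrate Diet |

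**Step 1: reproduce the plan's diet length.** 21 + 5 + 2 = 28 days, which matches the stated four weeks.

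**Step 2: confirm when the diet starts.**

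- Counting back from admission: 37 − 5 − 21 = Day 11.
- Counting forward: Day 11 + 21 = Day 32, when provided meals begin; Day 32 + 5 = Day 37, the admission.
- If the diet started at Visit 4 instead, the self-selected period would be 32 − 18 = 14 days, which contradicts the stated three weeks.
- The text agrees. Goals for the next three weeks are set at the first session, the counseling sessions from Day 11 onward review adherence, and the list for the days after Visit 4 has participants continuing the self-selected diet.

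**Step 3: delay of the sheet.** Delay = day of Visit 4 − Day 11.

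| Visit 4 held on | Delay | Share of 28 days |
|---|---|---|
| Day 16 | 16 − 11 = 5 days | 5/28 = 18% |
| Day 18 | 18 − 11 = 7 days | 7/28 = 25% |
| Day 20 | 20 − 11 = 9 days | 9/28 = 32% |

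Counting only the outpatient days (21 + 5 = 26), the nominal share is 7/26 = 27%, so the choice of denominator hardly matters.

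**Step 4: look for an earlier hand-out.** The Day 11 paragraph, the visit lists and Appendix A do not mention the sheet. The sentence under Potential Risks is the only place in the protocol that sets its timing.

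**Step 5: effect of the correction.** With the sheet given on Day 11, the delay falls from 7 days (5 to 9) to 0.

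**The case against.** The strongest reply is that active protections already cover the first week. Testing training sits in the Day 11 paragraph. Participants receive a meter with a staff demonstration, check ketones at least daily and glucose about every 12 hours, keep a log, and call if ketones exceed 0.6 mmol/L. That trigger works without any knowledge of symptoms. Staff call about twice a week, the glucose monitor is unblinded, insulin is adjusted with the medical team, and the hyperglycemia sheet has been in hand since Visit 2. The protocol also describes early symptoms as appearing several days before DKA, so daily testing should often catch a rise. All of this stands and keeps the point modest. It does not supply the missing item: the glucose monitor does not measure ketones, ketones need be checked only once a day, and the training is described only as training in testing. The symptom half of the contact rule covers the time between checks.

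Second, participants may learn about DKA from the consent form or the study-specific procedures. Neither is in the copy reviewed, so what they are told by Day 11 cannot be judged either way. The point therefore rests on the sheet's stated timing alone.

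Third, the Visit 4 label may be a slip. The protocol describes Phase 2 as Visits 4 to 8, so the authors may have meant the start of Phase 2 and overlooked that instruction begins at the end of Visit 3. This is plausible. It is still the operative text, and it is corrected in the same way.

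Fourth, because no visit list contains the sheet, staff might in practice hand it out on another day. That is fair, and it is a reason to tie the sheet to the Day 11 training rather than leave it only in the risk section.

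**Conclusion.** The concern holds. As written, the DKA sheet arrives about 7 days (5 to 9) after the diet begins, 25% (18% to 32%) of the nominal 28 days, for all 10 planned Phase 2 participants. This is the delay of one handout, partly offset by the other first-week protections. It is not an estimate of added DKA risk, and the data and analysis are untouched.

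Two assumptions apply. The diet starts directly after the Day 11 session, which the day count and the counseling text both support. The unexplained + 28 beside Day 11 in the Appendix A header does not alter the 7 ±2 day spacing between that session and Visit 4; a shift that moves both together leaves the delay unchanged. The mismatch between the two dates is certain; the 5-to-9-day range depends on the second assumption.

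**What to change.** In the Low Carbohydrate Diet entry under Potential Risks, change the timing of the DKA sheet from Visit 4 to Visit 3/Day 11, before the diet starts, and give it together with the ketone- and glucose-testing training at that session. Naming the sheet in the Day 11 paragraph of Study Visits as well would put it where staff look for the day's procedures.

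The cost is one visit label, plus one line of text if the Day 11 paragraph is also amended. The session already takes place, so no visit, procedure or expense is added.
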